## 2. RATIONALE FOR THE STUDY

### 2.1. Background and current management

Traumatic brain injury (TBI) is a major large public health and societal problem with an annual incidence of 262 per 100.000 patients in Europe. TBI is defined as an alteration in brain function, or other evidence of brain pathology, caused by an external force. Clinical severity of TBI lies on a continuum graded by the Glasgow Coma Scale score from which TBI has been classified in the broad categories of "severe (GCS 3-8)", "moderate (9-12)", and "mild (13-15)". Research has focused for a long time in the more severe forms of TBI, due to its more evident catastrophic consequences to life. However, mild TBI is the more frequent form of TBI (70-80% of all TBI), and therefore pose the greatest health care burden caused by TBI [1,2]. The population affected by TBI depends on the degree of development of the country, and as the population ages, the number of patients affected by TBI increases, specifically in this form of mTBI. The most frequent cause of mTBI nowadays is falls and this incises in the aged group of European population.

The initial management of mild TBI in the ED relies on performing a non-contrast brain CT if the patient meets specific conditions. Efforts have been made to optimize the indications for Brain CT scan after mTBI such as different clinical decision rules (CDRs) such as the Canadian Head CT rule[3] or the New Orleans criteria[4]. However the prevalence of CT detected abnormalities is less than 10% in patients with mTBI and a minority of these patients with intracranial lesions will require a neurosurgical procedure (1%).

Several aspects are in controversy in the management of patients with mTBI. In the ER[5-8], the need for performing or not a CT, the value of the CDRs and protocols used in the ER to select those patients in need of having a CT performed and the value of serum biomarkers for selecting these patients in need of further examination has been thoroughly studied[9-18]. The variability in the management of mTBI between different hospitals within a country and in Europe (16)(and publication in press from our group) implies that CDRs are not correctly followed by physicians attending these patients due to the complexity of these rules, the difficulty in actually applying them in certain conditions such as intoxicated patients, hearing loss or speech difficulties, and the insecurity many physicians and patients have to being discharged without a CT. As a consequence, up to 40% of CT scans obtained in the ER would actually not follow these CDRs. Therefore, the number of CTs performed for this condition is very high, with important consequences for health expenditure and radiation exposure to patients. This is also a specific and important problem for elderly patients. Intracranial changes that occur with aging as well as the increasing prevalence of comorbidities and antithrombotic medication use put the elderly at an increased risk of intracranial bleeding after low velocity falls. Most CDRs use age over 60 or 65 as one of the factors associated with use of CT scan after mTBI. Elderly patients are therefore at an increased risk of CT overuse as they suffer many times from recurrent falls and sometimes receive one CT for each fall.

## BRAINI2-IMPLEMENTATION STUDY

Patients with mTBI lesions are often hospitalised in the standard ward where neurological monitoring consists of repeated CT scanning and clinical exams. Patients without lesions on the initial head CT-scan are also hospitalised when their GCS score after CT scan is less than 15.

Additionally, elderly patients on anticoagulants or antithrombotic drugs are more frequently hospitalised due to physicians' concerns about potential deterioration. This determines a bigger number of unneeded hospitalisations for these patients.

Therefore, although CT scan plays a pivotal role in the management of mTBI, there is an unmet clinical need for an objective tool to optimize and guide indications for CT scan, reduce clinical practice variability, reduce patient radiation exposure and improve patient outcome prediction.

### 2.2. Blood Biomarkers in mTBI

Serum biomarkers have appeared as a possible solution for determining the need for CT in patients with mTBI. S-100B has been incorporated in one of the CDR (The Scandinavian mild head injury management guidelines)[17,18]. However, the use of this biomarker is restricted to Scandinavian countries and has not gained acceptance in any other country. There are specific concerns regarding its negative predictive value, the variation of its concentration regarding skin color or the increase in its concentration when there is systemic trauma[21,22]. GFAP and UCHL1 are two brain specific biomarkers that have recently been demonstrated to have in combination a very high negative predictive value for demonstrating lesions in CT and there is some data regarding their possible role in determining prognosis and even their ability to determine which patients could have lesions detectable in MRI[23].

Recently a new algorithm including blood biomarkers (GFAP and UCH-L1) has been proposed in the management of mTBI patients in Spain supported by different organizations and medical societies including the Spanish Neurosurgical Society. This algorithm has not yet been studied for its net benefit in reducing costs or the number of CTs prescribed. Additionally, there is no data on the time needed to provide accurate results available to the clinician. Nevertheless the recommended algorithm has been adopted and proposed by different medical societies, including the Spanish Society for emergency Medicine and the Spanish Society of Neurological Surgeons (SENEC). This algorithm will be adopted by the Department of Neurosurgery of this Hospital in order to implement this new solution.

### 2.3. VIDAS TBI

The VIDAS TBI assay is an automated, quantitative, enzyme-linked immunofluorescent assay (ELFA) for the detection of Ubiquitin C-terminal Hydrolase-L1 (UCH-L1) and Glial Fibrillary Acidic Protein (GFAP) in blood serum. The assay is to be used in conjunction with other clinical information, as an aid in the evaluation of adult patients with mTBI (with Glasgow Coma Scale score (15-13) within 12 hours of injury to assist in determining the need for a CT scan of the head. This assay has been assessed in the BRAINI study[24] and is now CE marked and FDA approved. There is no data regarding the practical use or real-world data including the use of the VIDAS GFAP&UCH-L1 assay.

### 3. STUDY OBJECTIVES AND OUTCOME MEASURES

#### 3.1. GENERAL OBJECTIVE

The general objective of BRAINI-2-Implementation Study is to assess the performance of the biomarkers GFAP and UCH-L1 in real life and to assess their safety of use when incorporated into the clinical management of the patient and to establish their acceptance and integration into an already accepted management pathway.

#### 3.2. PRIMARY OBJECTIVE AND OUTCOME MEASURE

The primary objective of the study is to evaluate the performance of the two biomarkers GFAP and UCH-L1 assay to rule out the need for CT scan after mTBI.

The primary outcome will be the result of brain CT. Performance of the test will be analysed, as described in the assay instruction for use, to rule out the need for a CT scan after mTBI.

CT results will be obtained following the usual management pathway, using local radiologist report to determine the presence of pathological findings. Patients in whom no CT will be performed (i.e.: some GCS 15 without RF and GCS 14 with negative biomarkers test), will be ascribed as CT negative for the analysis if there is no deterioration or further evaluation that determines the need for a CT for other reasons.

Both GFAP and UCH-L1 biomarkers will be tested by two separate immunological assays using the usual clinical management and pathway in the management of mTBI. The positivity thresholds for each of the biomarkers and the two biomarkers' combination were validated by the company Banyan Biomarkers in an independent study, ALERT-TBI [13] and confirmed by bioMérieux using the VIDAS TBI with the same ALERT-TBI cohort and with the BRAINI study. The test will be performed if the patient is included in the new management pathway of patients with mTBI incorporated in our hospital. If the patient is included in this pathway, the prescription of cranial CT will be performed following the results of the VIDAS TBI test obtained. Patients with GCS of 13 will receive both biomarkers and CT scan for their management. Patients not following the clinical pathway (GCS<13 or non TBI patients) will be excluded from the study and managed according to routine clinical practice.

The VIDAS TBI test interpretation as defined by the manufacturer, bioMérieux, takes into account the responses of the two biomarkers: the VIDAS TBI test is negative if the two markers GFAP and UCH-L1 are negative (below the previously defined threshold concentration for each of the biomarkers). The test is positive if at least one of the two GFAP or UCH-L1 biomarkers is

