## 5.2. STUDY TIMELINE AND PLANNED MANAGEMENT ALGORITHM

All patients with TBI admitted to the ER and with a GCS between 13 and 15 will receive a blood test for biomarker determination upon admission. All patients with GCS of 13 or with a focal neurological deficit on admission will receive a CT. CTs could be performed to GCS14 and 15, independently of the result of the combined test, but the results of the test will be taken into consideration to guide for prescribing a CT. The attending physician will be responsible for the management of the patient and will have to determine the reason to prescribe CT despite normality of the biomarker test. The management algorithm that is recommended is as follows:

Risk factors (RF) include:

- Loss of consciousness.
- Posttraumatic amnesia (anterograde or retrograde).
- Advanced age (over 65)
- Antithrombotic treatment including platelet inhibitors.
- Difficulty in assessing level of consciousness: Cognitive impairment, intoxication.
- Persistent symptomatology: Repeated vomiting, persistent headache.
- High energy or High-risk mechanism: Falls over one's height, car accident, pedestrian involved in traffic accident, or accidents in which other there are other seriously injured patients.

Data will be collected directly from a specified structured form in the electronic health record of the patient. All data will be pseudonymised. Information regarding follow up will be recorded from the electronic health record regarding new contacts with the hospital or need of further assessment.

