### 5.3. PARAMETER ASSESSMENTS

#### 5.3.1. Clinical parameters

1) Vital signs will be measured in the emergency department according to standard practice (GSC score, arterial blood pressure, heart rate, respiratory rate, body temperature, pulse oximetry). The presence of vomiting, nausea or headache will be recorded, as well as the presence of loss of consciousness. All recorded variables will be obtained following the standard of care of the workup of the mTBI patient established in the Hospital and no extra information will be obtained.

Secondary deterioration within the first week after TBI will be obtained by reviewing electronic medical history of the patient's and new contacts during this week with the ER, and is defined as follows:

- a decrease in GCS score of more than 2 points from the initial GCS score in the absence of sedatives
- a deterioration in neurologic status sufficient to warrant intervention, i.e. mechanical ventilation, sedation, osmotherapy, neurosurgical procedure or admission to the intensive care unit.
- Admission to a hospital ward exclusively related to deterioration of neurological condition due to TBI.

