## BRAINII2-IMPLEMENTATION STUDY

in patients with negative biomarkers, percentage of CT requested in patients with positive biomarker, percentage of pathologic CT in patients with positive biomarker, percentage of pathologic CT in patients with negative biomarker, percentage of patients requiring admission and percentage of second ED visit after discharge.

Finally, the de-identified data from the mTBI cohort will be obtained and transferred into a web based electronic CRF(eCRF) built on RedCap to be able to be analysed. The database in RedCap will contain pseudo-anonymised clinical information about the patients with mTBI from six months prior to the implementation protocol and information from six months of the implementation protocol.

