## 6. STUDY STOPPING RULES

### 6.1. STUDY STOPPING CRITERIA FOR A PARTICIPATING SUBJECT

Participants will be excluded from the study and replaced in case of a violation of an inclusion criterion, e.g. in the mTBI group: no mild TBI, no CT scan when the patient should have received one according to the study design, no blood sampling or after 12 hours post-injury.

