## 7. STATISTICAL CONSIDERATIONS

### 7.1. SAMPLE SIZE

The primary endpoint of the study is to replicate the diagnostic performance of the VIDAS TBI assay to predict whether the tested patient would be positive or negative from brain injury visible on head CT scan and to determine that implementation of the VIDAS TBI, in the standard of care of patients with mTBI, is not associated with serious side effects during the six-month period of the study. We expect to test during a six-month period around 1000 patients (from the 3500 patients with suspected TBI that are admitted to our hospital yearly approximately (data from discharge diagnosis of patients with TBI related diagnostic codes)). With this sample size and with an expected prevalence of 10% of CT positivity we expect to have at least 100 patients with positive CTs. With this sample size we expect to replicate the NPV of the BRAINI study with an expected lower bound of the 2-sided 95% CI greater than or equal to 97.0%.

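### Unscanned patients are scored CT negative although the test guides who is scanned, so the primary NPV is biased upward as a measure of CT-visible injury

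*Protocol*

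**What the plan says.** Section 3.2 takes the brain CT result as the primary outcome and states that "the prescription of cranial CT will be performed following the results of the VIDAS TBI test obtained". Patients who receive no CT "will be ascribed as CT negative for the analysis if there is no deterioration or further evaluation that determines the need for a CT". As examples it gives some patients with GCS 15 and no risk factor, and patients with GCS 14 and a negative test.

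Section 5.2 requires a CT for GCS 13 or a focal deficit. For GCS 14 and 15 the test result guides the decision, and the physician "will have to determine the reason to prescribe CT despite normality of the biomarker test".

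Section 6.1 excludes and replaces patients with "no CT scan when the patient should have received one according to the study design".

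Section 7.1 sets the aim of the test as to "predict whether the tested patient would be positive or negative from brain injury visible on head CT scan", and expects to "replicate the NPV of the BRAINI study with an expected lower bound of the 2-sided 95% CI greater than or equal to 97.0" per cent.

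Follow-up of unscanned patients is a review of electronic records with no added contact (5.1, 5.3.1, 5.3.3). Deterioration in 5.3.1 means a GCS fall of more than 2 points, a need for intervention, or "Admission to a hospital ward exclusively related to deterioration of neurological condition due to TBI".

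Among the dashboard indicators in 5.3.3 is the "percentage of pathologic CT in patients with negative biomarker".

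**The concern.** The index test helps decide who receives the reference standard, and missing reference results are then filled in with the value that agrees with a negative test. This is partial verification with favourable imputation.

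Clinical follow-up does not remove the problem. Section 5.3.4 counts contusions and petechial haemorrhages as CT positive, and such lesions need not meet any of the deterioration criteria in 5.3.1.

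Two things are at stake:

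- The same assay would show a higher NPV simply because fewer test-negative patients were scanned, that is, because physicians complied better with the algorithm. Compliance is itself a secondary objective (3.3.3).
- What is measured is the absence of injury found on CT or becoming clinically apparent during follow-up. That suits an implementation study, but it is not the target to which 7.1 ties the replication claim. A favourable figure would be read as showing more than it does.

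**Working it through.** **The plan's own figures.** 1000 patients × 10% prevalence = 100 CT positives, as 7.1 states. The 97.0% limit cannot be reproduced, because the protocol gives no expected NPV, sensitivity, specificity or number of test-negatives. It is attainable on plausible assumptions: with 900 CT negatives, specificity 40% and sensitivity 97%, there are 360 true negatives and 3 false negatives, and the lower limit for 360/363 is 97.6%.

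**Margin for error.** The exact (Clopper-Pearson) two-sided 95% lower limit reaches 97.0% with at most 1 false negative in 200 test-negatives, 3 in 300, or 5 in 400. A few unseen lesions therefore decide the result.

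**Who is unscanned.** Section 6.1 removes patients who lack a required CT. Those left unscanned should therefore be mainly test-negative patients with GCS 14-15. This is an inference, since the algorithm figure is not shown.

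**Bias formula.** Let *w* be the probability that a test-negative patient with a lesion is scanned, and *d* the fraction of unscanned lesions that surface in follow-up. The rule in 3.2 counts only the share

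*s* = *w* + (1 − *w*)*d*

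of the missed lesions, so

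apparent NPV = 1 − (1 − true NPV) × *s*.

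Since *s* ≤ 1, the apparent NPV is never below the true one. They are equal only if no unscanned test-negative patient has an undetected lesion.

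**Share of missed lesions counted** (assumed *d* from 0.01 to 0.25):

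| *w* | *s* |
|---|---|
| 0.5 | 0.505-0.625 |
| 0.2 | 0.208-0.400 |
| 0.1 | 0.109-0.325 |

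**Effect with 300 test-negatives.** Counted false negatives ~ Binomial(300, (1 − NPV) × *s*), and the 97.0% limit is reached with 3 or fewer. Apparent NPV is for *w* = 0.2. Example: true NPV 98% with *s* = 0.4 gives 1 − 0.02 × 0.4 = 99.2%.

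| True NPV | Apparent NPV | P(limit ≥ 97.0%), all scanned | *w* = 0.5 | *w* = 0.2 |
|---|---|---|---|---|
| 96% | 98.4-99.2% | 0.2% | 6-14% | 29-76% |
| 98% | 99.2-99.6% | 15% | 48-64% | 78-96% |
| 99% | 99.6-99.8% | 65% | 88-93% | 97-99.6% |
| 99.5% | 99.8-99.9% | 93.5% | 98.5-99.3% | ≥ 99.7% |

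The bias at *w* = 0.2 is 2.4-3.2, 1.2-1.6, 0.6-0.8 and 0.3-0.4 points respectively.

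**If scanning targets risk.** Suppose 20% are scanned but patients with lesions are scanned at twice the average rate (*w* = 0.4). The probabilities become 10-28%, 58-77%, 91-97% and 99.0-99.7%.

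**Other numbers of test-negatives.** At true NPV 98%, going from all scanned to *w* = 0.2 moves the probability from 9% to 52-80% with 200 test-negatives, and from 19% to 90-99% with 400.

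**Sensitivity, if reported, is inflated too.** Take 100 lesions, 10 of them missed by the test, 80% of test-negatives unscanned and none surfacing. Two misses are counted, and 90/92 = 97.8% appears in place of 90.0%.

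**The case against.** The strongest reply is that 3.2 states the rule openly, and that its primary objective is ruling out the need for a CT. For that objective, CT or clinical follow-up is a recognised reference. Misses that matter clinically are also covered: further evaluation leading to a CT counts, records are reviewed, second visits are tracked, and safety is a principal objective of its own. On this view only a wording mismatch with 7.1 remains, and the additional analyses belong in the SAP.

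On size, every driver is assumed. A true NPV of 96% with 300 test-negatives means 12 misses among 100 expected positives, a sensitivity of about 88%, which may be pessimistic for a test whose NPV section 2.2 calls very high. More surfacing weakens the effect. With 300 test-negatives, 10 lesions and 80% unscanned, 30% surfacing leaves about 4 counted misses and a lower limit of 96.6%, so the limit is not wrongly reached.

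Much of this stands. The composite reference is legitimate, the size is uncertain, 97.0% is a stated expectation and not a pass/fail rule, and the bias is small if the true NPV is 99% or more. None of it changes the direction or supports the CT-based claim in 7.1. Nor is this a detail left to the SAP: the protocol itself fixes both the scoring rule and the target that the rule does not measure.

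**Conclusion.** The concern holds and should be corrected before the primary result is interpreted. As a measure of CT-visible injury, the NPV under 3.2 is biased upward whenever an unscanned test-negative patient has a silent lesion. The direction follows from the algebra.

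The size depends on the true NPV, the share of test-negatives scanned, whether those scans select higher-risk patients, and how many lesions surface. The protocol gives none of these, and no BRAINI NPV. Over the range examined, the bias is large enough to decide whether 97.0% is reached if the true NPV is near 96-98%, and modest at 99% or above. The dashboard indicators in 5.3.3 reveal part of the problem, but the denominator for pathologic CT in test-negatives is not stated and neither indicator is tied to the primary NPV.

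**What to change.** In 3.2 and 7.1:

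1. Name the imputed measure *NPV for intracranial injury found on CT or clinically apparent during follow-up*. Apply the 97.0% expectation to that measure, and do not present it as replicating a CT-based NPV. The follow-up window needs one definition, since 3.2 gives two weeks, 5.3.1 one week and 5.3.3 ten days.
2. Report beside it the NPV among CT-scanned test-negatives with its exact interval, and the share of test-negatives scanned. Build on the 5.3.3 indicators, and state scanned patients as the denominator for pathologic CT in test-negatives.
3. Add bounds in which unscanned test-negatives have lesions at *k* = 0, 0.5, 1 and 2 times the scanned rate. For example, with 300 test-negatives, 60 scanned and 1 lesion found, 1 − (1 + 240*k*/60)/300 gives 99.7%, 99.0%, 98.3% and 97.0%. In the same example the rule in 3.2 gives 99.7% (lower limit 98.2%), and the scanned-only figure is 98.3% (lower limit 91.1%).
4. Note that CTs after a negative test are discretionary and need a reason (5.2). They probably select higher-risk patients, so the scanned-only NPV may be too low. Weighting for verification bias is optional, and only if there are enough events.

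The cost is wording, one stated denominator and one small table, with no change to patient care or data collection. The downside is a wide interval for the CT-verified NPV and a less favourable CT-based claim: no misses in 60 scanned gives a lower limit of 94.0%, and at least 122 scanned with none missed are needed to reach 97.0%.

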## BRAINII2-IMPLEMENTATION STUDY

positive (beyond the threshold concentration). This test has been already tested in a large number of European patients and has presented good safety and reliability profiles.

To determine the safety of the new protocol all information regarding the neurological status of the patients in relation to mTBI will be analyzed up to two weeks after the mTBI, specifically neurological deterioration, need for further observation of the patient or admission or need for treatment(medical or surgical) related to mTBI.

In order to determine the reduction of CT scans obtained with this new protocol, absolute numbers and proportions of patients finally scanned using this new protocol will be compared to the reference management of a similar number of patients during a similar historical period(i.e. data from the previous six month for patients attended for mTBI at Hospital 12 de Octubre).

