1. STUDY SUMMARY

TITLE	Blood Biomarkers to improve management of mild traumatic BRAIN Injury implementation study
RUNNING TITTLE	BRAINI2 Implementation study
GENERAL OBJECTIVE	To assess the applicability and added value of a new clinical management pathway for patients with mild TBI presenting to the emergency department (ER), including the use of an in vitro diagnostic assay measuring the biomarkers GFAP and UCH-L1 in the serum, within the first 12 hours post-injury, to rule out the need for CT scan in mild TBI patients.
PRINCIPAL OBJECTIVE	
 
1) To evaluate the diagnostic performance of the VIDAS TBI (GFAP&UCH-L1) test in determining the need for CT-scan in patients with mild TBI admitted to the ER of Hospital 12 de Octubre.
 
2) To determine the safety of a management protocol including the use of the VIDAS GFAP&UCH-L1 test for patients with mTBI, in terms of complications or unforeseen neurological deterioration following the injury.
 
3) To estimate the reduction of CTs achieved using the biomarker test, by comparison with the management of TBI during the six months preceding the study (reference pathway).
 

PRINCIPAL OUTCOME	
Abnormal CT scan at admission in the ER
 
Deterioration: need for hospital admission or surgery due to TBI in the first week after TBI
 
Number of CTs prescribed in the management of mild TBI patients in the ER

PRINCIPAL OUTCOME MEASURES	
 
1) Diagnostic performance of the biomarker test
 
2) Proportion (%) of neurologic deterioration within 1 week post-TBI
 
3) Proportion (%) of CT scan prescribed in the ER over the period of the study for patients with mTBI
 

SECONDARY OBJECTIVES	
 
2.1) To determine the different times involved in the management of mild TBI patients and the effect of using the combined VIDAS test.
 
2.2) To establish differences in direct costs in the management of mild TBI in Hospital 12 de Octubre.
 
2.3.) To assess the compliance of physicians to the proposed algorithm.
 

SECONDARY OUTCOMES	
 
2.1) Time from admission to discharge. Time from admission to sample obtention. Time from venipuncture to availability of biomarker results.
 
2.2) Directs costs associated with mTBI management in the ER.
 
2.3.) Compliance with proposed algorithm.
 

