SECONDARY OUTCOME MEASURES	
 
2.1) Time differences with respect to reference group
 
2.2) Cost difference comparing before and after the implantation of the biomarker test.
 
2.3) Proportion (%) of cases in which management follow the proposed algorithm
 

METHODOLOGY	
The study will compare the different outcome measures between a historic group obtained 6 months before the initiation of the new management protocol and the group of patients admitted in the ER with a diagnosis of a mTBI after the initiation of the new bundle of care.
 
The combined GFAP&UCH-L1 test has been included in the new bundle of care of mTBI for the management in the ER of all patients with mTBI. In summary the test will be performed to all patients with mTBI admitted to the ER of Hospital 12 de Octubre and included in the new management pathway of patients with mTBI incorporated in our hospital. All patients suffering a mTBI(GCS 15-13) and admitted within 12 hours of the TBI will be included in this pathway. If the patient is included in this pathway, the prescription of cranial CT will be performed following the results of the VIDAS TBI test if the patient has had a significant TBI and a GCS of 14 or 15. Those patients with GCS of 13 or a focal neurological deficit will receive both biomarkers and CT for their management during the study period. The VIDAS TBI test interpretation as defined by the manufacturer, bioMérieux, takes into account the responses of the two biomarkers: the VIDAS TBI test is negative if the two markers GFAP and UCH-L1 are negative (below the previously defined threshold concentration for each of the biomarkers). The test is positive if at least one of the two GFAP or UCH-L1 biomarkers is positive (beyond the threshold concentration). This test is already CE marked and has already been tested on a large number of European patients and has demonstrated good safety and reliability profiles.

STUDY TYPE	Protocol evaluation Implementation Study
STUDY DESIGN	Implementation study with prospective data collection with a control reference historic group
STUDY POPULATION	Mild TBI patients with significant brain trauma admitted in the ER of Hospital 12 de Octubre

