INCLUSION CRITERIA	
-All adult patients suffering mild TBI:( Defined by at least criterion a) and d) and one or more of the other criteria)
 
    a) The presence of a plausible traumatic mechanism observed/or related by the patient's recount of the injury event.
 
    b) Presence of one or more clinical signs attributable to brain injury: Loss of consciousness immediately following injury, alteration of mental status immediately following the injury, posttraumatic amnesia or any neurological abnormality.
 
    c) At least two acute symptoms related to the injury: feeling confused or disoriented, headache, nausea, vomiting, dizziness, vision problems, memory problems, emotional lability or irritability.
 
    d) a GCS between 15 and 13, at least 30 minutes after injury.
 
-Blood sample obtained ≤12 h after injury and ideally before any imaging prescription.

EXCLUSION CRITERIA	
 
· GCS 3-12 on admission
 
· Age Below 18 years
 
· Time of injury unknown
 
· Time to injury exceeding 12 hours
 

BRAINI2-IMPLEMENTATION STUDY

	
 
· Primary admission for non-traumatic neurological disorder (e.g., stroke, spontaneous, intracranial hematoma)
 
· Penetrating head trauma
 
· Patient with mechanical ventilation from the trauma scene or prehospital management
 
· Venipuncture not feasible
 

NUMBER OF SUBJECTS	The implementation study will last for 6 months. The number of patients that are normally treated for this pathology is around 3000 patients each year. During the 6 months of the study around 1000 patients will at least be triaged for mild TBI
STUDY CENTRES	Hospital 12 de Octubre
PROVISIONAL CALENDAR OF THE STUDY	
 
- Start of inclusions: Jan 2025
 
- Inclusion period: 6 months
 
- End of inclusions: July 2025
 
- Length of participation of each subject: 2 weeks
 
- Total length of the study: 6 months
 

STATISTICAL ANALYSIS	
Outcome assessment
 
CT scan status will be attributed to each study participant based on the presence of intracranial lesions. Local CT reading will be used.
 
Outcome assessors will be blind to the participant biomarker status.
 
Quality control outcome assessment will be performed over the study period via sequential intra/inter observer agreement assessment.

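### On the section 11 calendar, the six-month historical reference for CT reduction most naturally falls on October 2024-March 2025: three of its months are training and deployment, and none shares a calendar month with the study period

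*Protocol*

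**What the plan says.** Principal objective 3 in the study summary (section 1) is to estimate the fall in CT use "by comparison with the management of TBI during the six months preceding the study (reference pathway". The matching outcome measure is "Proportion (%) of CT scan prescribed in the ER over the period of the study for patients with mTBI". The secondary time and cost comparisons use the same historical group.

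The reference window is described in several places, always relative to some event and never by date:

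- Section 1, principal objective 3: the event is the study.
- Section 1, methodology: a "historic group obtained 6 months before the initiation of the new management protocol".
- Section 3.2: CT use is to be "compared to the reference management of a similar number of patients during a similar historical period(i.e. data from the previous six month".
- Section 3.3.2 (costs): the event is implementation of the new protocol.
- Section 5.3.3 (database): six months before the implementation protocol, set beside six months of the implementation protocol itself.

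Two calendars, both headed as provisional, could turn these into dates:

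- Section 1: "Start of inclusions: Jan 2025", "End of inclusions: July 2025", "Total length of the study: 6 months".
- Section 11: staff training and technology deployment in January-March 2025, inclusions from April to September 2025, total length 12 months.

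**The concern.** The CT-reduction objective is a before-after comparison, so the choice of the six earlier months decides who the controls are. Section 3.2 calls for a similar historical period. The window that follows most naturally from section 11 departs from that in two ways.

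First, half of it is the period in which staff are trained in the new pathway and the technology is put in place. If physicians began to order CTs differently in those months, CT use in the reference would already be partly reduced, and the measured reduction would be too small.

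Second, it covers autumn and winter while the study covers spring and summer. Any seasonal difference in case mix or emergency-room practice would be inseparable from the effect of the pathway, and it could act in either direction.

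The cost and time comparisons draw on the same group and carry the same exposure.

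**Working it through.** **Inputs.** Starts of inclusion: January 2025 (section 1) and April 2025 (section 11). Inclusion period: 6 months in both. Training and deployment: January-March 2025 (section 11). Reference length: six months (sections 1, 3.2, 3.3.2, 5.3.3). Whole months are used because no start days are given.

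**Step 1, the plan's own end dates.** April 2025 plus 6 months gives April-September 2025, which agrees with section 11. January 2025 plus 6 months gives January-June in whole months. The July end in section 1 fits only if inclusions start after 1 January.

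**Step 2, which event starts the clock.** Section 5.3.3 gives the implementation protocol a length of six months. In section 11 the only six-month block is the inclusion period. Implementation is therefore most naturally April-September 2025, and the six months before it are October 2024-March 2025. A second reading remains possible: the 12-month total in section 11 could make January 2025 the start of the study, and principal objective 3 counts back from the study. That would give July-December 2024.

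**Step 3, the windows compared.**

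| Basis | Reference window | Training/deployment months inside | Calendar months shared with inclusions |
|---|---|---|---|
| Section 11, before inclusions (natural reading) | Oct 2024-Mar 2025 | 3 of 6 | 0 of 6 |
| Section 11, before training | Jul-Dec 2024 | 0 of 6 | 3 of 6 (Jul, Aug, Sep) |
| Section 1 calendar | Jul-Dec 2024 | none stated | at most 1 (Jul) |

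In days, the natural reading has 31 + 28 + 31 = 90 training and deployment days out of 92 + 90 = 182, or 49%.

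**Step 4, bounds on dilution (natural reading only).** Let D be the true fall in the CT proportion, w the share of reference patients seen in January-March 2025, and f the fraction of D already present in those months. The reference proportion is lowered by w x f x D, so

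measured reduction / true reduction = 1 - w x f.

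With even volume, w = 0.5:

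- f = 0 (no change during deployment): 1 - 0 = 1.00.
- f = 1 (full effect from the first day of training): 1 - 0.5 = 0.50.

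If w were 0.4 to 0.6 (an assumption), the lower bound would be 1 - 0.4 = 0.60 to 1 - 0.6 = 0.40. The documents give no value for f.

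**Step 5, season.** No month of October-March occurs in April-September, so season and period coincide completely. The protocol gives no monthly volumes, case mix or CT rates, so no size can be put on this.

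**The case against.** Both calendars are provisional. A definition relative to the start is sensible while the start may move, and exact extraction dates can be left to a statistical analysis plan. All of that stands, and the absence of dates would not be a finding on its own.

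A reader might infer more from the conflicting calendars: that two teams could extract control groups differing in half their patients, about 500 of about 1000, because the two windows share only October-December 2024. The documents do not support this as an analyst's choice. The study has one centre and will have one actual start, so one calendar will simply be out of date. The figure counts patients who differ between schedules and is not an error in an estimate.

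A reader might also infer that the reference is contaminated, or that the reduction will be halved. No passage shows that CT ordering changed, or that the test was used on patients, in January-March 2025. The summary says the test "has been included in the new bundle of care of mTBI", but it gives no date, and section 2.2 puts adoption of the algorithm in the future. The mixed tenses prove nothing about the reference months. The 50% figure is a logical extreme.

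What the objection does not remove is the window itself. Reading section 5.3.3 as equating implementation with the inclusion months settles much of the ambiguity, but it settles it in favour of the window that contains the deployment months.

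**Conclusion.** The point holds as a correction that should be made to the comparator of a principal objective. On the section 11 calendar the plan most naturally yields a reference in which 3 of 6 months are training and deployment and 0 of 6 match the study period by calendar month. The month counts assume whole months and the section 11 dates.

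The consequence is a risk and not a demonstrated bias. Dilution would understate the reduction, so it works against the study's claim. Its lower bound of 50% needs even volume and the full effect throughout deployment. Seasonal confounding could go either way and cannot be sized.

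The diagnostic-performance objective and the sample-size reasoning in section 7.1 do not use the historical group and are unaffected.

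**What to change.** 1. Reconcile the calendars in sections 1 and 11.
2. Use one anchor for the reference in sections 1, 3.2, 3.3.2 and 5.3.3: the six months ending before training and deployment begin. On the section 11 calendar this is July-December 2024. Written as a rule, it moves with the actual start. It keeps six months of patients and also precedes the start date in section 1.
3. Where records are comparably coded, add April-September 2024 as a same-season sensitivity comparison, which shares 6 of 6 calendar months with the inclusions in section 11.

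The cost is a dated filter in the health-record extraction and a few wording changes. It is cheaper before the database described in section 5.3.3 is built, since a later change would alter that dataset.

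There are downsides. On the section 11 calendar the main reference would end three months before inclusions, which admits slightly more secular drift. Older records may also be less structured, because section 5.3.3 does not date the unified diagnostic code or the form. That is the reason to keep April-September 2024 as a sensitivity comparison only.
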